In case of a positive outcome (i.e. mere confirmation of our published results), the major advantage of nutrition therapy will be its relatively low cost while still affecting morbidity and mortality significantly. This can be practically achieved by redefining the dietician's task. The patient's own active participation in the decision making process is an important surplus in well-being and overall treatment. In combination with decreased morbidity and mortality the benefit of the patient can be found on every level.

Investigator(s)

PI and head of department of nutrition:

[name] [name], PhD: [contact]

Intensive Care UZ Brussel

Co-investigator:
[name], PhD: [contact]
Diabetes Clinic UZ Brussel

Sponsor *If applicable*

Baxter
Nutricia

Departments/laboratories involved in the study
Department of Nutrition: [contact]
Department of Intensive Care:
[contact] or [contact]
Department of Oncology: [contact]

Introduction

Background

Cancer is a disease with a high prevalence and incidence worldwide, and often incurable because the diagnosis is made in an advanced stadium. Nevertheless, 50% of patients survive on average 10 years nowadays (accounting for all cancers together). This, however, does not necessarily equals a state of being cured from cancer. On the other end of the spectrum there are patients with a very poor prognosis from the beginning, regardless of treatment. The financial drawback is that the costs for treating cancer worldwide are the highest of any disease, accounting for nearly one trillion euro per year.

One major cause for a poor prognosis is the presence of malnutrition, due to a decreased intake, caused by the patient's symptoms. Symptoms can vary greatly, but are usually of gastrointestinal nature (nausea, vomiting), although general weakness and even depression can be present, all caused by advanced disease itself or by therapy (typically chemotherapy). Advanced disease is also marked by an increased resting energy expenditure, due to the tumor's induction of a hyperkatabolic state of the body. This will cause the clinical entity called "cachexia" and will eventually be responsible for the patient's demise. Although cachexia is usually referred to as a body mass index (BMI) of < 20, in cancer a broader definition is used, whereby a weight loss > 5% over a period of 6 months is sufficient for the diagnosis, regardless of BMI (Fearon K, Nature Reviews Clinical Oncology, 2013).

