96 patients per cancer group (48 controls and 48 nutrition therapy), supplemented with 20% per group to take dropouts into account.

Inclusion criteria

- > 18 years
- Male and female
- CRC or NSCLC before chemo- or radiotherapy is started (naive to treatment), but surgery may already have been performed
- CRC or NSCLC relapse > 3 months after initial oncologic therapy
- Oncologic cachexia (undesired weight loss > 5% in less than 6 months)
- Written informed consent / ability to give informed consent

Exclusion criteria

- concomitant second malignancy
- uncertainty of diagnosis of CRC or NSCLC
- patient unfit for chemotherapy
- patient unfit for radiotherapy
- patient unfit for surgery
- palliative treatment or terminal patient (life expectancy < 3 months)
- patient already participating in another study
- Pregnancy / lactation
- Any other pathology present that causes the patient to be unfit for oncologic therapy (e.g. end-stage renal failure, severe COLD, severe heart failure)
- Unable to adhere to protocol instructions (e.g. language barrier)
- Investigator's uncertainty about the willingness or ability of the patient to comply with the protocol requirements
- Participation in any other studies involving investigational or marketed products concomitantly or within two weeks prior to entry into the study

Replacement of subjects

In case of dropout, subjects will be censored on the Kaplan-Meier curves.

[figure not shown]
Restrictions and prohibitions for the subjects

None.

Procedures

See below, to be performed at the oncology consultation.

Flowchart

systematic overview of the study: planned tests per visit of the subjects

Expected total duration of the trial: 2 year (inclusion).

Supervising MD during the tests: Principal Investigator: [name] or co-investigator: [name].

Randomisation/blinding

Computerized randomization, validated for clinical trials, are used.

Prior and concomitant therapy

See "Inclusion and Exclusion criteria". All other concomitant therapy is allowed.

Study analysis

Sample size calculation

The statistical power was calculated based on the pilot trial.

Analysis of the samples

Outcome parameters:

• Body weight
• BIA Bio-Electrical Impedance Analysis
• Blood Pressure
• Blood Sample Analysis
• Caloric and Nitrogen intake
• Indirect Calorimetry
• Sensewear ®
• Body weight
• BIA Bio-Electrical Impedance Analysis
• Blood Pressure
• Blood Sample Analysis
• Indirect Calorimetry
• Body weight, mortality, morbidity.

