- Primary: weight stabilisation, morbidity and mortality
- Secondary: Quality of Life (QoL 36)

Statistical analysis

2-tailed, paired t-tests will be used for statistical analysis.

Quality control and quality assurance

The quality control is performed by the certified and experienced research unit of the Intensive Care Department.

Publication policy

All rights belong to the PI and thus to the VUB/the UZ Brussel.

Protocol Amendment dd 12/06/2017

Background:

Due to lack of patients with 5% weight loss in 6 months and, by consequence, very low inclusion rate, it was decided to amend the protocol. To achieve this, a special cooperation with the department of Radiotherapy was established. The service sees many patients who lose weight during radiotherapy, partly because of cancer-related cachexia, but mostly due to the mucositis caused by radiotherapy itself, losing > 10% of their initial body weight (at the start of their therapy). This is especially seen in cancers of head and neck, oesophagus and stomach. Radiotherapy is performed on working days and treatments typically last 5-7 weeks (depending on indication).

Amendment:

- Inclusion of patients with colorectal, lung and pancreatic cancer will be changed to: Inclusion of patients with lung, gastric, oesophageal, head and neck and pancreatic cancer
- 5% weight loss over the past 6 months will be changed to: patients with the aforementioned cancers where radiotherapy will be part of their treatment (or will be the entire treatment)
- Duration of intervention of 3 months will be changed to: duration of intervention for the entire period of radiotherapy
- After recalculation of statistical power, only 48 patients will be needed instead of 96. With correction for dropouts, this will become 60 patients instead of 120. This means 30 controls and 30 patients in the intervention group.
- The amendment will be added to the registration at *clinicaltrials.gov*.

The procedure and flowchart will remain unchanged. Analysis of the data will remain: in whole, per cancer and per sex (the latter two criteria requiring 60 patients in each group).

Protocol Amendment dd 19/09/2017

Background:

The study has seen much more inclusions and is running well thanks to the previous amendment. Due to a typo, the colorectal cancer group was unfortunately omitted. Also, the absolute difference of survival in the TiCaCo trial after one year was similar to that after the second year.

Amendment:

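### Since June 2017 the trial can pool patients with and without more than 5% pre-entry weight loss, while the stated analysis makes no use of that prognostic factor

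*Protocol*

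**What the plan says.** The Protocol's Background defines cachexia in cancer by weight history: "a weight loss > 5% over a period of 6 months is sufficient for the diagnosis, regardless of BMI". The Inclusion criteria applied that definition as an entry rule: "Oncologic cachexia (undesired weight loss > 5% in less than 6 months". Every patient enrolled under this rule was therefore above the threshold.

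The amendment of 12/06/2017 was made for the stated reason "Due to lack of patients with 5% weight loss in 6 months and, by consequence, very low inclusion rate". It replaces the rule as follows: "5% weight loss over the past 6 months will be changed to: patients with the aforementioned cancers", provided that radiotherapy is some or all of the planned treatment. The amendment of 19/09/2017 restores colorectal cancer and leaves the other inclusion criteria as they were. The June amendment describes weight loss in the newly recruited population as arising "partly because of cancer-related cachexia, but mostly due to the mucositis caused by radiotherapy itself".

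On analysis, the June amendment says: "Analysis of the data will remain: in whole, per cancer and per sex". The Statistical analysis section names two-tailed paired t-tests. On allocation, the Randomisation/blinding section says only: "Computerized randomization, validated for clinical trials, are used". Weight stabilisation, morbidity and mortality are the primary outcomes. After the amendment 48 evaluable patients are needed, or 60 with dropouts (30 per arm).

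**The concern.** While the old rule applied, restriction kept prior weight loss within a narrow band: all patients had lost more than 5%. The amendment lifts the restriction and puts nothing in its place. The analysis is expressly carried over, with groupings by cancer and sex but not by prior weight loss, and a t-test has no place for a covariate. Because the rule was dropped for want of patients who met it, later recruits must be expected to include many who do not.

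Two things are at stake. First, the Background itself treats malnutrition as a major reason for poor prognosis and cachexia as an eventual cause of death. A factor that the protocol regards as prognostic is thus left unadjusted in a small trial with weight and mortality among its primary outcomes. Second, the title and objective concern cachectic patients, whereas the pooled estimate now averages over patients who are cachectic by the protocol's definition and patients who are not.

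**Working it through.** **Inputs from the protocol.** 48 evaluable patients (24 per arm), 60 with dropouts (30 per arm), and a 20% dropout allowance. The figures behind the power calculation are not given beyond a reference to the pilot.

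**Inputs assumed.** Share of patients with more than 5% prior loss: 30-50%. Correlation r of prior loss with on-study weight change: 0.3-0.5. The protocol gives neither. It also does not say how many patients entered before 12/06/2017, so the extent of mixing cannot be computed.

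**1. The plan's own figure.** 48 / (1 - 0.20) = 60, and before the amendment 96 / (1 - 0.20) = 120. Both reproduce. The base figure of 48 cannot be checked, because alpha, power, effect and SD are not stated. With two-sided 0.05, 80% power and independent arms, 24 per arm detects (1.96 + 0.84) × sqrt(2/24) = 0.81 SD.

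**2. Chance imbalance of at least 20 percentage points.** Two exact calculations were made: simple allocation (two independent binomials), and a fixed number of such patients split at random between equal arms (hypergeometric).

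| Per arm | Prevalence | Binomial | Hypergeometric |
|---|---|---|---|
| 24 | 30% | 0.155 | 0.111 |
| 24 | 40% | 0.184 | 0.238 |
| 24 | 50% | 0.193 | 0.148 |
| 30 | 30% | 0.120 | 0.158 |
| 30 | 40% | 0.147 | 0.187 |
| 30 | 50% | 0.155 | 0.196 |

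The range is 11-24%. The hypergeometric column is uneven because counts are whole numbers. With 24 per arm, 20 points is 4.8 patients. An odd total (19 at 40%) reaches that with a difference of 5, while an even total (14 or 24) needs 6.

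**3. What such an imbalance does.** If prior loss is worth 0.3-0.8 SD of the outcome (assumed), a 20-point imbalance moves the estimate by 0.2 × 0.3 = 0.06 to 0.2 × 0.8 = 0.16 SD. The standard error of a two-arm difference at 24 per arm is sqrt(2/24) = 0.29 SD, so the shift is 0.21 to 0.55 of one standard error.

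**4. What adjustment is worth.** Adjusting removes a share r² of the residual variance: 0.09 at r = 0.3 and 0.25 at r = 0.5. The equivalent unadjusted size is 48 / (1 - r²), that is 48 / 0.91 = 52.7 and 48 / 0.75 = 64. In terms of power, starting from 80% at 24 per arm, r² of 0.10, 0.20 and 0.30 gives 84%, 88% and 92%.

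**5. What a split at 5% can show.** The standard error of the treatment-by-cachexia interaction is sqrt(2/(24p) + 2/(24(1 - p))). At p = 0.5 this is sqrt(2/12 + 2/12) = 0.58 SD; at p = 0.3 it is sqrt(2/7.2 + 2/16.8) = 0.63 SD. The interaction detectable with 80% power is 2.80 times that, or 1.6-1.8 SD. An interaction of 0.81 SD would be found with 25-29% power.

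**The case against.** The strongest reply is that nothing here is biased. Concurrent randomisation balances prior weight loss in expectation, and a valid unadjusted between-arm comparison already carries chance imbalance in its standard error. This stands. The shift in step 3 stays near half a standard error at most, and imbalances of that size occur in a minority of trials. A reader might infer that the factor is uncontrolled or that the primary results are distorted; the documents do not support either.

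A reader might also take prior weight loss for the main driver of further loss. The amendment says otherwise and attributes loss in the new population chiefly to mucositis. Nor does the protocol ever call prior weight loss an effect modifier; it was an entry criterion. That the effect differs with prior loss is plausible but not stated. A split by prior loss would not separate the two mechanisms cleanly either, because mucositis arises during radiotherapy and can affect both kinds of patient.

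Third, a statistical analysis plan may exist and could add covariates, the single sentence on randomisation does not exclude stratification, and the visit flowchart is not shown. This stands in part: one cannot say that weight history goes uncollected, or that allocation ignores it. But the point does not rest on silence alone. The amendment makes a positive statement that the analysis stays as it was, while removing the rule that had kept all patients above the threshold. An unseen plan does not undo that.

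Last, the prevalence and correlation are assumed, and the interaction will be imprecise. Both are true. They limit the claim to a modest one and make the subgroup result exploratory.

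**Conclusion.** The point holds as a matter of precision and of interpretation. After 12/06/2017 the stated analysis can pool patients with and without the protocol's own definition of cachexia, and it names no use for a factor that the Background treats as prognostic. On the assumed 30-50% prevalence, an imbalance of at least 20 points has roughly an 11-24% chance. On the assumed correlation of 0.3-0.5, adjustment raises the effective size from 48 to about 53-64; the gain depends wholly on that correlation. The pooled estimate no longer refers specifically to the cachectic patients of the title and objective. Adjustment does not change that, and the split at 5% addresses it only in an exploratory way. This is a worthwhile, inexpensive improvement to the plan, and its absence does not make the between-arm comparison invalid.

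**What to change.** - Record percentage weight loss over the 6 months before entry for every patient. For those already enrolled, take it from the file.
- Prespecify that percentage as a baseline covariate in between-arm models for weight change and for mortality. Use it as a continuous variable.
- Report the treatment effect for more than 5% against 5% or less, with the interaction and confidence intervals. Label this exploratory and state its precision (interaction standard error about 0.6 SD at 24 per arm).
- Optionally, use the same 5% split as an allocation factor for patients still to be randomised.

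The cost is one history item per patient and one model term, plus the interaction term for the exploratory report. The downsides are that some earlier weights will be recalled rather than measured, and that the subgroup estimate will be imprecise and must not be read as confirmatory.

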Study design

randomized controlled double-blind parallel-group multi-centre study

Medication/device *If applicable*

Not applicable (enteral and parenteral nutrition, commercially available)

The subjects

Number of subjects

- Colorectal cancer (CRC) st. III - IV (TNM system) with cachexia
- Non-small cell lung cancer (NSCLC) st. III - IV (TNM system) with cachexia

120 subjects in each group, 60 controls and 60 Nutrition Therapy patients, based on statistical power. 20% extra patients were added to this number to account for dropouts.

Investigational group (Group A)

At the time of diagnosis, patients will immediately be screened and started with Nutrition Therapy if assigned to group A. This regimen will stay in place for 3 months, after which a switch will be made towards normal dietary counselling. Nutrition Therapy can be given orally, parenterally or via tube feeding, depending on the patient's status and aims at matching caloric Intake with Resting Energy Expenditure. Moreover, a switch between these modalities is possible during these 3 months. Afterwards, standard dietary counselling will be given during the remainder of the study. Follow-up will last 1 year. If one year after the last enrolment the study shows a large difference with the control group, the study will be stopped for ethical reasons.

Reference group (Group B)

At the time of diagnosis, patients will immediately be screened and started with standard dietary counselling for 2 years if assigned to group B. Dietary intervention can be orally, parenterally or via tube feeding, depending on the patient's status. Moreover, a switch between these modalities is possible during these 3 months. Follow-up will last 1 year. If one year after the last enrolment the study shows a large difference with the control group, the study will be stopped for ethical reasons.

Both Groups:

Oncological treatment will be performed at the discretion of the participating specialists, following the ESMO guidelines. Although an open label study, the oncologic treatment will not be related to the dietary regimens.

Inclusion is to take place in a period of one year. The duration of the study for each subject from randomisation to end of treatment is three months and a follow up period of nine months, for a total of one year per patient. Afterwards, analysis will take place.

Power calculation:

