- Colorectal cancer patients are still to be included. Otherwise, nothing changes concerning inclusion criteria.
- The follow-up will be shortened from 2 years to one year.
- The amendment will be added to the registration at *clinicaltrials.gov*.

Protocol Amendment dd 05/02/2019

Background:

The study needs 48 inclusions that remain in the study until the end. However, the number of dropouts is too high, severely compromising the study's statistical power. Therefore, an inclusion surplus of 20 - 25% is required.

Amendment:

- The inclusion period will be expanded to 31/12/2019 or the inclusion of 60 patients (including dropouts), whichever is sooner.
- The amendment will be added to the registration at *clinicaltrials.gov*.

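### The June 2017 amendment sets a whole-study requirement of 48 against a per-cancer requirement of 96, so it understates the cut, and 60 patients in total cannot supply the subgroup sizes it says are needed

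*Protocol*

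**What the plan says.** The base Protocol lists two cancers, colorectal and non-small cell lung, under *Number of subjects*, and then gives "120 subjects in each group, 60 controls and 60 Nutrition Therapy patients, based on statistical power". *Power calculation* fixes the unit: "96 patients per cancer group (48 controls and 48 nutrition therapy), supplemented with 20% per group to take dropouts into account". *Sample size calculation* names the source: "The statistical power was calculated based on the pilot trial".

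The amendment of 12/06/2017 widens the tumour sites, replaces the weight-loss criterion by planned radiotherapy, and ties the length of the intervention to the radiotherapy period. On size it says "After recalculation of statistical power, only 48 patients will be needed instead of 96", then "With correction for dropouts, this will become 60 patients instead of 120", then "This means 30 controls and 30 patients in the intervention group". It keeps analysis of the whole set, by cancer and by sex, and adds that the last two call for 60 patients in each group.

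The amendment of 05/02/2019 says "The study needs 48 inclusions that remain in the study until the end" and closes inclusion at 60 patients, dropouts counted, or at the end of 2019 if that comes first.

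**The concern.** The numbers being replaced (96 and 120) applied to each cancer. The numbers replacing them (48 and 60) apply to the trial. A reader of the amendment alone would think that the trial had been halved by a power calculation. In the base Protocol, 48 was the size of one arm in one cancer; it is now both arms over all sites.

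Two things are at stake. First, the trial is presented as a validation of a 20-patient pilot. If 48 is taken as the number that statistical power requires, a non-significant result may be read as a failure to confirm the pilot, when it may only reflect a much smaller trial. Second, the analyses by cancer and by sex are kept with a size condition that the trial can no longer meet, so they could be reported as if they had been adequately sized.

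**Working it through.** **1. The plan's own figures.** With 20% dropout, enrolled = evaluable / (1 − 0.20).
- Base Protocol, per cancer: 96 / 0.8 = 120, or 60 per arm. This matches.
- Amendment: 48 / 0.8 = 60, or 30 per arm enrolled and 24 per arm evaluable. This matches.

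The dropout arithmetic is sound. Neither 96 nor 48 can itself be re-derived, because the Protocol states no significance level, target power, effect size, variance or event rates.

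**2. The units, side by side.**
- *Power calculation*: "96 patients per cancer group (48 controls and 48 nutrition therapy". The unit is one cancer.
- Amendment of 12/06/2017: 48 evaluable, 60 enrolled, 30 per arm. The unit is not stated.
- Amendment of 05/02/2019: "The study needs 48 inclusions that remain in the study until the end", with inclusion closed at 60. The unit is the whole study.

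**3. Like for like.**
- Two cancers: 2 × 96 = 192 evaluable; 2 × 120 = 240 enrolled.
- New total against the old total: 48 / 192 = 0.25 and 60 / 240 = 0.25.
- New total against one cancer: 48 / 96 = 0.50.
- The June 2017 amendment describes the earlier population as three cancers (it adds pancreatic). On that count the old total is 3 × 96 = 288 evaluable and 3 × 120 = 360 enrolled, and the new total is 48 / 288 = one sixth.

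**4. The subgroup condition.** The amendment asks for 60 patients in each group for the analyses by cancer and by sex.
- By sex: 2 × 60 = 120 patients.
- By cancer: the June 2017 amendment names five sites and the amendment of 19/09/2017 restores colorectal, making six. 6 × 60 = 360 patients.
- Available: at most 60 in total, an average of 60 / 6 = 10 per site.

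**5. Illustration of power.** Assumptions, none of them from the Protocol: two-sided 5%, two-sample t-test, original power of 80% to 95% at 48 per arm, and an unchanged standardised effect d.

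Normal approximation at 80%: d = (1.960 + 0.842) × √(2/48) = 0.572. At 24 per arm, d × √(24/2) = 0.572 × 3.464 = 1.981, and power = Φ(1.981 − 1.960) = 0.51.

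The noncentral t gives:

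| Power at 48 per arm | d | Power at 24 per arm | Ratio |
|---|---|---|---|
| 80% | 0.578 | 50% | 0.63 |
| 85% | 0.618 | 55% | 0.65 |
| 90% | 0.669 | 62% | 0.69 |
| 95% | 0.743 | 71% | 0.75 |

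The difference detectable with 80% power rises from 0.58 SD at 48 per arm to 0.83 SD at 24 per arm. At 90% power it rises from 0.67 to 0.96.

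**The case against.** The strongest defence is that the amendment reports a recalculation for a different trial. The population, the entry criterion and the length of intervention all changed, and the background says that radiotherapy patients lose more than 10% of body weight. The Protocol's title treats stable weight as the route to lower morbidity and mortality, so a larger expected effect on all the primary outcomes is consistent with the plan's own reasoning. A smaller sample could then be correct. This stands. It means that 48 cannot be called wrong, and that the power figures above are conditional on an effect which the sponsor may have revised. The inputs may also be recorded outside the Protocol, so their absence is not the defect.

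A second defence is that 60 might be a per-cancer figure, since the amendment's remark on subgroups uses 60 for each group and 30 per arm fits either reading. Read alone, the June 2017 text allows this. The February 2019 amendment does not, because it gives 48 completers and a limit of 60 for the study. If 60 were nevertheless meant per cancer, that limit would contradict it, so the passages would still need to be reconciled.

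A reader might go further and infer that the amended trial has about half the power of the original. The documents do not support that. They give no power for either design, and half the sample is not half the power: under an unchanged effect the ratio to the per-cancer design is 0.63 to 0.75. It comes near one half only against both cancers pooled (96 per arm) with 80% planned per cancer, where the normal approximation gives 0.508 / 0.977 = 0.52.

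**Conclusion.** The point holds as a misstatement of scope. The amendment sets a whole-study 48 (60) against a per-cancer 96 (120). The real reduction is from 192 to 48 evaluable and from 240 to 60 enrolled on the two cancers in the base Protocol, a quarter of the original; it is larger if three cancers are counted. Separately, the trial cannot supply the 60 patients in each group that the amendment attaches to its analyses by cancer and by sex. Both conclusions rest only on the Protocol's own numbers and on the February 2019 amendment for the scope of 48 and 60.

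No stated loss of power follows. The fall to about 50% or 62% is an illustration under assumed inputs. The only test that the Protocol names is a paired t-test, so the two-sample calculation is not the sponsor's. Nor is 192 beyond dispute, since the Protocol describes the earlier population as two cancers in one place and three in another.

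**What to change.** Correct the wording of the June 2017 amendment, and the registry entry to match. No added enrolment is asked for.

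- Say that 96 evaluable and 120 enrolled applied to each cancer group, and that 48 and 60 are now totals over all tumour sites, with 24 evaluable and 30 enrolled per arm. Settle whether the earlier population was two or three cancers before quoting an original total.
- Give the inputs of the recalculation (outcome, effect, variance or event rates, significance level, test) and the power they yield at 24 evaluable per arm. If no such calculation supports 48, say that the reduction was made for feasibility. The illustrative 0.83 SD should not be entered as the sponsor's figure.
- Say that the analyses by cancer and by sex do not reach the size set for them and are exploratory.
- Say that a non-significant result is inconclusive and does not refute the pilot.

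Weight, morbidity and mortality stay as primary outcomes; this point gives no reason to change that. The cost is wording, and a statement of power that will be less favourable than the present one.

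### The June 2017 amendment changed duration, entry criterion and tumour types in a running trial but kept one whole-sample analysis, so the overall estimate mixes two protocol versions

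*Protocol*

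**What the plan says.** The main text of the protocol (The subjects, Investigational group) sets the regimen at three months: "This regimen will stay in place for 3 months, after which a switch will be made towards normal dietary counselling". Its inclusion criteria require "Oncologic cachexia (undesired weight loss > 5% in less than 6 months", in colorectal or non-small cell lung cancer.

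The amendment of 12/06/2017 alters three things together:

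- **Duration:** "Duration of intervention of 3 months will be changed to: duration of intervention for the entire period of radiotherapy". Its background says that radiotherapy "treatments typically last 5-7 weeks (depending on indication".
- **Entry criterion:** "5% weight loss over the past 6 months will be changed to: patients with the aforementioned cancers where radiotherapy will be part of their treatment". Radiotherapy alone also qualifies.
- **Tumour types:** gastric, oesophageal and head and neck cancers come in. Colorectal drops out and is restored by the amendment of 19/09/2017.

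The reason given is a shortage of eligible patients and, "by consequence, very low inclusion rate". The same amendment reduces the target from 96 to 48 (120 to 60 with dropouts) and closes with: "Analysis of the data will remain: in whole, per cancer and per sex". The amendment of 05/02/2019 keeps a single count, extending inclusion to the end of 2019 "or the inclusion of 60 patients (including dropouts), whichever is sooner".

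**The concern.** A slow inclusion rate, followed three months later by a report that inclusion had picked up, implies that some patients were randomised under the old version. No restart is described, and nothing takes those patients out of the analysis or the target. The amendment confirms a whole-sample analysis straight after changing who is treated and for how long.

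The per-cancer analysis does not separate the versions. Lung cancer spans both, and so does colorectal cancer once restored.

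The protocol itself gives reason to expect the versions to differ. Its background treats cachexia as a driver of poor outcome, whereas the amendment attributes weight loss in the radiotherapy population chiefly to mucositis and only partly to cachexia. Weight and mortality are both primary outcomes. A single overall effect therefore has no clear reference population or duration. By chance, early patients may also fall unevenly between two arms of 30.

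**Working it through.** **The plan's own figure.** With a 20% dropout allowance, N/(1 - 0.20) gives 48/0.8 = 60 and 96/0.8 = 120, as stated. The base figures of 48 and 96 cannot be reproduced, because no effect size, variability, event rate, alpha or power is given.

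**Contrast in duration.** Three months is 365.25/4/7 = 13.0 weeks. Against 5-7 weeks, 13/7 = 1.86 and 13/5 = 2.6, so the amended duration is 38% to 54% of the former one.

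**Early share (assumed).** The protocol gives no count. Taking 4, 8 or 12 of 60, f = 4/60 = 7%, 8/60 = 13% or 12/60 = 20%.

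**What pooling does to the estimate.** Let the effect be E1 under the old version and E2 under the amended one, with r = E2/E1. The pooled effect is f·E1 + (1 - f)·E2. Relative to E2 this is 1 + f(1/r - 1).

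| Early patients | r = 0.5 | r = 0.75 | r = 1 |
|---|---|---|---|
| 4 of 60 | +7% | +2% | 0 |
| 8 of 60 | +13% | +4% | 0 |
| 12 of 60 | +20% | +7% | 0 |

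The values of r are assumptions. If r exceeded 1, the pooled effect would understate the amended-version effect instead.

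**Chance imbalance.** Suppose 8 early patients, 30:30 overall, and allocation not balanced over time. The number falling in one arm is hypergeometric:

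P(X ≤ 2) = (5,852,925 + 61,074,000 + 258,292,125)/2,558,620,845 = 0.127; two-sided 0.254.

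A 6:2 split means 6/30 = 20% of one arm against 2/30 = 7% of the other, a gap of 13 percentage points. If mortality differed between versions by 10 to 30 points (assumed), the arm difference would shift by 0.133 × 10 = 1.3 to 0.133 × 30 = 4 points.

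**Cost of the amended-version estimate.** Against all 60, its standard error grows by √(60/56) = 1.04, √(60/52) = 1.07 or √(60/48) = 1.12.

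**The case against.** The strongest reply is that the analysis sentence lists levels of analysis (everyone, by tumour, by sex) and does not decide to pool versions. Adjustment by version could sit in a statistical analysis plan that is not shown. The first part is a fair reading of the sentence. Even so, a whole-sample analysis includes the early patients unless something removes them, and nothing does. The amendment also affirms that analysis after making the changes, so this is more than a detail left for later.

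Several further replies stand, and they limit the point:

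- **The early group may be tiny.** With a handful of patients the pooled effect is essentially that of the amended version. A reader might infer that the result would belong to neither version; with the count unknown, the protocol does not support that.
- **Randomisation was concurrent.** A reader might infer bias. Protocol version cannot favour one arm systematically, and chance imbalance is already covered by the nominal error rate. Blocking over time, if used, would make 6:2 splits much rarer than 25%.
- **It is one strategy.** Both versions match intake to expenditure, and the protocol's objective section equates the original three months with active cancer treatment. To call them two different interventions goes too far: they are two durations.
- **The later patients are not unselected.** They were chosen for planned radiotherapy in cancers where weight loss is expected. The protocol does not show which group has the worse baseline risk.
- **Timing of entry is not a clean contrast.** The original criteria also admitted relapse more than 3 months after initial therapy, and the amendment does not alter the treatment-naive criterion.

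**Conclusion.** The point holds in a limited form. The plan keeps one overall analysis and one target across two versions that differ in duration, entry criterion and tumour types. The resulting estimate is a weighted average whose weights depend on an unreported number. On the assumed range of 4 to 12 early patients, the distortion of the amended-version effect is 2% to 20% if the later effect is half to three quarters of the earlier one, and nil if the two are equal. The 25% chance of a 6:2 or worse split rests on exactly 8 early patients and on allocation not balanced over time.

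This concerns the meaning of the estimate and, secondarily, precision and chance imbalance. It is not a claim that the comparison is invalid or its type I error inflated. It is worth changing because the remedy needs no new patients or data.

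**What to change.** 1. State whether patients randomised before 12/06/2017 count toward the 48/60, and report how many there are in each arm.
2. Stratify the overall between-arm comparison of each primary outcome by protocol version at randomisation, or adjust for it. The only named test, a paired t-test, has no place for such a term, so a between-group method is needed: for example a linear model with a version term for weight, and a version-stratified survival comparison for mortality.
3. Report the estimate in patients randomised under the amended version beside the overall one. A separate estimate in a few early patients would be uninformative and need not be interpreted.
4. Limit the conclusion to the version that the data mainly support.

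The cost is one stratification term, slightly lower precision, and naming a between-group method in place of the paired test. Randomisation dates should already be on record. The passages on duration in the main text and the amendment should also be reconciled; no view is taken here on which is right.
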